- 4) Data management: Charting Once the frameworks are set up, the data from each transcript will be 'charted' or summarised into them. The summaries will be written in the third person and aim to capture the key views of the participant under each of the themes represented by columns. The researchers doing the charting will remain as close as possible to the language used by the research participants. As the data is charted, researchers will identify key verbatim quotes from the transcripts and add these to the framework in italics to be used in the report if needed. Charting will be done by several researchers who will all read and quality assure each other's charting to ensure a consistent and comprehensive approach. Throughout the data management stage, researchers will be mindful of revisiting the thematic framework and adjusting it where needed. For example, adding new sub-themes that were previously not discussed or collapsing themes together where necessary.
- 5) Analysis and interpretation The first stage of analysis is descriptive. This will involve looking at each theme in turn and exploring the range of views held under that theme with a view to developing categories. This will be done by grouping the views into clusters and exploring the properties of each of these clusters until clear categories can be developed. Given the nature of the feasibility study and the size and likely diversity of the sample, it is highly likely that the majority of the analysis will be descriptive and aim to clearly map out the range and diversity of views that exist within each participant population on the key areas relevant to the research questions. However, where possible the researchers will proceed to a higher level of analysis and aim to look for patterns and linkages in the data. This stage will be facilitated by the framework approach as it easily allows the researcher to look both within and across cases to see how different parts of the data set are connected. The sorts of patterns and linkages that might be explored include links between particular experiences of the intervention and how those link to views or outcomes, or the research team may explore links between particular characteristics of the participants and their views and experiences. Where possible, the

research team will then go on to look for explanations for the categories and linkages that have been found. Throughout the analysis process, the research team will remain in contact with each other, sharing and testing emerging findings and ensuring that the analysis process remains rooted in the data.

6. Cost evaluation - data collection and reporting

We will report the cost of delivering the intervention in the final report, following YEF costing guidance. We will:

- Use a bottom-up costing approach and break costs down into: prerequisites, set-up costs, and recurring costs.
- We will report the total cost for a typical single cohort receiving the intervention for one round of delivery and the costs per participant for one round of delivery, assuming full compliance.
 Depending on heterogeneity in costs across cohorts, we will either report average costs, or select a case which we think is most representative of the costs we expect to be incurred in future, typical rounds of delivery.

The organisations and practitioners involved in delivery are Barnardo's and the programme developer ISII. To report cost at the end of this study, we have produced a template for these organisations to complete, covering staff costs, equipment/materials costs, programme procurement costs, and buildings and facilities costs.

We expect most costs to fall within the following two categories:

- Staff cost: cost of practitioners, supervisors, and managers involved in delivering Barnardo's.
- Programme procurement costs: the cost for ISII to train and supervise staff, as well as to produce and provide the programme-specific materials required to deliver the programme.

7. Planned outputs

The outputs of this overall package of work and their timings are dependent on the outcomes of stage of the work. All findings will be published at the point the project concludes.

Regardless of the outcome of the pilot study, the Lab will provide a short report to the YEF outlining the key findings and observations of the pilot study. This will make a formal conclusion as to whether GenPMTO can be feasibly evaluated in the UK, and recommend whether the evaluation should progress to Stage 4 (efficacy stage).

If the pilot study concludes that GenPMTO is sufficiently feasible to evaluate in the UK and ready to progress to a full-scale RCT, we will not publish these findings externally at the completion of the pilot study. We will instead report the full findings of the pilot study at the end of the *entire* study, once the efficacy stage is completed. This report will contain findings and/or recommendations from the feasibility study, pilot trial and/or full-scale efficacy trial of GenPMTO. The Lab will share the findings more broadly where appropriate (and with the express permission from Barnardo's and YEF), such as

in presentations, blogs and the Behavioural Insight Team's (BIT) annual report. The primary audience of YEF's website is practitioners and researchers interested in reducing young people's involvement in Violence.

If the pilot study concludes that GenPMTO is not sufficiently feasible to evaluate in the UK and not ready to progress to a full-scale trial, then these findings will be published externally at the completion of the pilot study in the form of a publicly accessible report, which will include the key findings of the feasibility and pilot studies.

8. Ethics and data protection

Ethics

Overview

This trial was self-assessed as being high risk due to the inclusion of high-risk participants in the form of vulnerable young people. As a result we sought ethical approval from an independent panel of external experts with experience of working with vulnerable children and experience with safeguarding and child protection. We sought input from our panel twice - once, at the beginning of the feasibility study, and again during the transition from feasibility to pilot RCT.

The independent ethics review committee (ERC) reviewed the following information:

- Ethical review form
- Consent forms and information sheets for young people and parents/caregivers of young people
- Topic guides
- Outcome surveys
- Safeguarding and distress protocol
- A specification of the approach to randomisation and nature of intended control group.

The ERC discussed any issues raised by the research with The Lab with the aim of finding solutions that meet ethical requirements. The reviewers and the project manager agreed solutions to any outstanding issues, and the resulting changes to the way the project is being implemented have been included on the ethics form. The ERC was happy to approve the project with the inclusion of these amendments.

If there are substantial changes while the research or evaluation is being implemented, the ethics form will be revised and the revisions agreed with the ERC.

Informed Consent

All participants will be asked to provide written consent to participate in the pilot study for ethical purposes, before data collection, randomisation and interviews take place. Participants will be provided with an information sheet to inform them of what to expect from their involvement in the pilot study.

We will invite all caregivers to complete outcome surveys. All participants will be informed of their right to withdraw their consent at any point during interviews and/or data collection sessions. We will make

it clear to participants that we will use their information to inform the findings of our evaluation, which will be incorporated into a report, or other publicly publishable materials. However, no identifying information will be disclosed in any such materials.

We will also inform participants that they may be able to withdraw their data from the study, up until approximately 6 months after the end of the study. At this point their data will be deleted from our systems, and anonymised information will have already been incorporated into reporting, or other publicly publishable materials.

Safeguarding

Safeguarding means protecting the health, wellbeing and human rights of children and at-risk adults, enabling them to live safely, free from abuse, violence and neglect. During the pilot study, we will protect adults-at-risk by following a strict safeguarding and distress protocol. Before any interviewing or surveying with vulnerable groups, any researcher will:

- Undergo, and obtain, an **enhanced DBS check**.
- Complete the NSPCC's Introduction to safeguarding and child protection training.
- Review the Nesta Group Safeguarding Policy and the GenPMTO Child safeguarding issues and Risk Assessment.
- Review the GenPMTO Safeguarding and distress protocol.

If, during any research activity, a participant discloses anything that leads a researcher to believe that they themselves, or someone else, might be at risk of harm, they will follow these steps:

- Step 1: Is there an immediate risk of harm to the interviewee or others?
 - If yes: they will call the police or other emergency services as soon as possible and follow up with an emergency report to the Nesta Group Chief People Officer (The Lab's Designated Safeguarding Lead) and the project's qualitative lead.
 - \circ If no: proceed to step 2.
- Step 2: Establish an understanding of what has happened
 - They will keep questions to the minimum necessary to ensure a clear and accurate understanding of what has been disclosed. The researcher will only ask questions to help establish whether the participant is at risk of harm. They will not make allegations or lead them to make allegations.
 - The researcher will ask the young person or at-risk adult whether anyone is aware of what they have disclosed e.g. are the parents/caregivers aware of it. If the concern is about a pre-existing mental health condition that is known to the caregivers or medical professionals (e.g. the adults GP), for example, this would not represent a safeguarding concern that would need to be reported.
 - If you notice something concerning, which hasn't been disclosed: they will ask open questions to establish if there is an explanation e.g. "that looks like a big bruise. Can you tell me what happened?"
- Step 3: Make a written record
 - The researcher will note down what has been said, any physical evidence that is available including injuries or the personal state of the participant.
- Step 4: Inform the participant
 - If the researcher considers that there is a risk, they will inform the participant that they need to tell the Lab's designated safeguarding lead. They will explain that a safeguarding lead is the person in an organisation that's responsible for dealing with concerns to people's safety.
- Step 5: Report the concerns

- Nesta Group Chief People Officer (the Lab's Designated Safeguarding Lead) and the project's qualitative lead.
- The researcher will be available to the designated safeguarding leads to assist with further assessments, including whether cases need to be escalated to other parties such as the child protection services.

Data protection

We have followed appropriate data protection processes in accordance with BIT processes, including completing a Data Protection and Security Checklist and Data Protection Impact Assessment, which have both been reviewed and approved by BIT's legal team.

The Lab will store and handle all data securely and confidentially in line with requirements of the UK GDPR, and Data Protection Act (2018), including that Personal Data shall be processed lawfully, fairly and in a transparent manner that ensures the security of the Personal Data. It is initially proposed that only the Lab research team will have access to data collected as part of the evaluation. However, it is expected that in order to review the fidelity of the implementation of GenPMTO, and to coach and certify practitioners, ISII will require access to data from the sessions in which the practitioners deliver the programme to caregivers. Given that most ISII training staff are based in the USA, Barnardo's have established a Data Sharing Agreement with ISII, with the Lab overseeing this process.

For the duration of the evaluation, the Lab will be the data controller who also processes data. This means that the Lab is responsible for deciding the purpose and legal basis for processing data. The legal basis is "legitimate interest". Article 6(1)(f) of UK GDPR states that "processing is necessary for the purposes of the legitimate interests pursued by the controller or by a third party except where such interests are overridden by the interests or fundamental rights and freedoms of the data subject which require protection of personal data, in particular where the data subject is a child."

The Lab has determined there is a genuine purpose to process this data. This data will inform the necessary evidence around what works to improve caregivers' skills and strategies, which in turn, improves positive behaviours, relationships and life outcomes of young people, particularly those at risk of, or who have engaged in, violent behaviours. Data processing is necessary to complete a robust evaluation. The Lab does not consider that collecting and gathering data for this trial will interfere with individuals' interests, rights or freedoms. The data subjects will include; at-risk youth, caregivers of at-risk youth, the developer team at ISII and the delivery team at Barnardo's.

During this trial, data will be stored on secure, password-protected and encrypted network drives (hosted by BIT). Access to the data will be restricted to the relevant members of the project team involved in this evaluation.

All data shared with BIT will be processed in line with its data protection policy. A summary of this policy can be found in Annex C. In the analysis, BIT will promote data quality and security through the following measures.

- All variables will be clearly named, coded and labelled before analysis
- Checks on the data received will be carried out for valid values, range, and consistency against already held data
- Any modifications to datasets will be recorded in the analysis code, which will be well-annotated
- Original raw datasets will never be amended
- Access to the project data will be restricted to project personnel
- All data stored by BIT will be backed up

In case a Personal Data Breach occurs despite the mitigations in place, project team staff will deal with the security incident without undue delays. All Personal Data Breaches (or suspected Personal Data Breaches) will be reported to BIT's Data Protection Officer as soon as a project team member becomes aware of one (including if this is outside of office hours) by contacting the Data Protection Officer directly and by completing a Data Incident Notification Form. Staff will not attempt to investigate a Personal Data Breach themselves but will take steps to contain the Personal Data Breach as quickly as possible. Such steps might be taken prior to reporting the incident to the Data Protection Officer where this is reasonable and necessary to protect Data Subjects and mitigate the potential impact of the Personal Data Breach.

Data management

All quantitative and qualitative data will be stored in a secure Google Folder where access is restricted to only researchers conducting the analysis. Data will be deleted upon completion of the project 6 months after the conclusion of the project.

Quantitative data

Survey data

We will use SmartSurvey to collect the survey data. SmartSurvey produces a spreadsheet where one row is a survey response. This will be used to code the survey outcomes using the methods outlined in the outcome measures table.

Surveys will ask participants to record their name. This enables us to link survey responses with demographic data and other outcome measures. Once survey responses have been linked, participants' names will be removed.

Programme administrative data

Barnardo's is responsible for providing us with the programme administrative data. All data shared with the lab by Barnardo's will be received via a secure transfer link (Virtru or Quatrix).

Programme administrative data includes the *referral data* and the *programme delivery data* (e.g. attendance sheets, fidelity checklists). *Referral data* will be collected via an online form (located on FormAssembly) completed by borough staff. Barnardo's will download the data in a spreadsheet and share the relevant data with the lab. *Programme delivery data* will be collected via Barnardo's , and shared with the lab.

Qualitative data

Interview transcripts

Interview recordings will be uploaded to McGowan for transcription. All interview recordings will be transcribed verbatim to ensure accuracy and facilitate subsequent analysis. Transcripts will be anonymised by assigning unique identifiers to each participant, replacing their names or any identifying information. Transcripts, observation notes, and any additional relevant documents will be securely stored in a password-protected file area. Access to the data will be restricted to only project team members involved in the analysis. Recordings will be deleted upon completion of the project.

9. Racial diversity and inclusion

The Lab is committed to conducting research in which equality, diversity and inclusion principles are firmly embedded across all stages of evaluation, from the design, recruitment, data collection, and analysis.

Groups included in the programme and evaluation

The Lab will work with Barnardo's to monitor for inequalities within the referral and recruitment processes to ensure that no demographic group is unduly excluded from access to the study and the GenPMTO programme. At all stages, we will monitor whether certain demographic groups are underor over-represented in referrals to the programme by referral agencies. This may occur due to unconscious bias within referral agencies, and/or because the study or GenPMTO programme is viewed by referral agencies as unsuitable for families with certain demographic characteristics. In either case, the Lab and Barnardo's would seek to investigate this further in consultation with referral agencies.

Similarly, at all stages the Lab will work with Barnardo's to monitor whether the rate of acceptance to the trial (i.e. families accepting the offer to participate in the RCT) varies across certain demographic groups. If this is the case, the Lab and Barnardo's will seek to investigate why this is the case, and whether the programme content and/or delivery needs to be adapted to ensure equality of acceptability and access.

Inclusivity during recruitment and programme delivery

The Lab will work with Barnardo's as programme delivery partner to ensure that inclusive practices are central to the *recruitment process* and that participant wellbeing is promoted by:

- 1. Being considerate of the sensitivity of the topic area during recruitment
- 2. Providing caregivers with welcoming information documentation, which provides all necessary information about data security, anonymity and the reasons for undertaking research, in plain English
- 3. Offering a flexible and varied range of times for introductory (and other) sessions, and the option of attending sessions remotely via video-link, allowing different groups and individuals the opportunity to participate.

Inclusivity during data collection

The collection of data directly from caregivers will occur via caregiver surveys and caregiver interviews. To ensure that the principle of inclusivity is adhered to during this process, the Lab will work with Barnardo's to:

- 1. Use inclusive and accessible language in all survey and interview questions and guidance;
- Ensure that sufficient numbers of either Lab and/or Barnardo's staff will be present at in-person sessions where caregiver surveys are being administered, to provide assistance or instruction as required;
- Strive for equality of access by enabling online (remote) participation in caregiver surveys and interviews. Access issues could include a lack of time during the day to attend sessions, or distance from an in-person session.
- 4. Training for researchers: Prior to conducting interviews, researchers will complete the NSPCC's Introduction to safeguarding and child protection training.

Wellbeing and safety during surveys and interviews

The Lab is conscious that families who engage in the evaluation could be vulnerable to negative and stressful impacts of the research process. The Lab will work to ensure the wellbeing and psychological safety of individuals during data collection by:

- 1. Designing interview questions to minimise harm and maximise comfort: The Lab will maximise wellbeing and minimise harm during surveys and interviews by (i) structuring questions to build in complexity and difficulty to increase comfort as rapport to develop, (ii) depersonalising questions to elicit comfort and stronger answers (e.g. instead of 'what do you hate about X', ask 'If you had a magic wand, what 3 things would you change about X?"), (iii) being aware of tension discomfort or distress during the interview, repeating that the interview can be stopped may help participants and repeatedly ask if they want to continue, (iv) ensuring that researchers are aware of places to signpost participants and offer this information, and (v) auditing the questions for their sensitivity within the context before the interview.
- Allowing the participants to choose their environment for participating: Where possible the Lab will allow the interviewees to make decisions about the survey and interview setting(s)
 at their home, a public place or over the phone, enabled by the online conference format.
- 3. **Reminding participants of anonymity and data security**: The Lab will seek to minimise anxiety for caregivers by reminding them that the process is fully anonymous and that all identifiable information will be removed from the transcripts and report.

10. Risks

Risk	Impact	Likelihood	Mitigation
Low participation in research activities by caregivers (including differential attrition and higher drop-out from the control group)	High	Medium	 Providing incentives to the control and treatment groups (£20 per completed survey); Ensuring that evaluation activities are designed to be low-impact in terms of burden and time (including offering flexibility in terms of how surveys are completed); Where needed, utilising the relationships that Barnardo's and referring practitioners have built with participants to facilitate access and cooperation. We will inform participants with sufficient notice
			 about planned survey activities. In particular we will attempt to maintain contact throughout the trial period particularly with control group participants, to remind them of their participation in the study and upcoming opportunities to receive their vouchers. We will monitor rates of attrition, and whether there are differences in rates of attrition based on parent/caregiver ethnicity, gender, age, and

We have identified the following risks, focusing specifically on the evaluation:

· · · · · · · · · · · · · · · · · · ·			
			in terms of baseline outcomes.
Unrepresentative business-as-usual offer	High	Medium	 Given variation in the level of need of families referred into the project, and variation in how, why, and by whom they've been referred, we would expect the business-as-usual for these families to naturally involve a mix of services, and for the business-as-usual offer not to be dominated by high-intensity programmes similar to GenPMTO. We have emphasised in all communications with Boroughs that we do not want control groups to receive an artificially restricted or artificially boosted offer in the context of this trial, and that control group participants should receive services that the Borough would have provided to these caregivers in the absence of the GenPMTO project. We will monitor what services the control group receive.
Non-compliance by staff with random assignment	High	Low	 Our delivery team and Boroughs understand and are on board with the requirements of running a randomised controlled trial. We will monitor compliance through attendance lists to identify any accidental crossover from control group to treatment group.
Spillover between treatment and control participants	Medium	Low	 The likelihood of spillover is deemed to be low given that the programme is covering a large geographical area with over 200,000 residents. Moreover, the programme is intensive and involves a variety of roleplay exercises and activities to support parents in developing and implementing new parenting strategies. We believe that any effects are likely to emerge as a result of participation in the full programme, and don't expect that sharing information from the programme would provide the same benefits. Finally, if spillover does occur, we believe this would lead to an improvement in outcomes for the control group, which would likely cause an underestimation of the effect size of the intervention, which is relatively tolerable as a risk (when compared to an overestimation).
There is turnover at the Lab, such that we do not have sufficient capacity to collect and analyse data, and manage the overall project	Medium	Low	 Should core members of the evaluation team be taken ill, or depart, EYV Lab is able to quickly draw on the resource pool from BIT, which consists of over 150 staff members. Key decisions and files are stored in secure folders on Google drive. These will help team members to aid with knowledge transfer and

	 onboarding of new staff, should other core EYV Lab staff depart. Thorough trial documentation (including this protocol) will allow for the trial to be evaluated and the results analysed, even if key staff are redeployed or depart.
--	---

11. Timeline

Activity	Cohort	Target dates	Description
Recruitment	All cohorts.	November '24 to June '25	Rolling recruitment over a 7 month period.
Baseline data collection and randomisation	1	December '24	-
	2	January '25	
	3	February '25	
	4	March '25	
	5	April '25	
	6	May '25	
	7	June '25	
GenPMTO delivery	1	December '24 to March '25	_
	2	January '25 to April '25	
	3	February '25 to May '25	
	4	March '25 to June '25	
	5	April '25 to July '25	
	6	May '25 to August '25	
	7	June '25 to	

		September '25	
Post-test data collection	1	March '25	-
	2	April '25	
	3	May '25	
	4	June '25	
	5	July '25	
	6	August '25	
	7	September '25	
Analysis	-	March '25 to October '25	Ongoing data management and analysis throughout study as cohorts begin to end.
Reporting and progression decision to stage 4 efficacy	-	October '25	-
6-month follow-up data collection	1	September '25	-
conection	2	October '25	
	3	November '25	
	4	December '25	
	5	January '26	
	6	February '26	
	7	March '26	

NB: We will submit data to YEF's archive at the point of study completion.

Annexes

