The quantitative monitoring criteria used to monitor evaluability-related objectives are described in Table 2 below. While the criteria below offer guidance for the progression of the evaluation on the basis of quantitative assessments, these will also be complemented by qualitative measures, such as ongoing practitioner feedback and interviews with practitioners and caregivers. Overall, we will not establish a deterministic rule about how many green-, amber-, and red-rated criteria would justify/prohibit progression, but instead will use the criteria to support a balanced judgement, weighting the importance of each criteria in the round.

The monitoring criteria specified below were developed iteratively in consultation with both Barnardo's and ISII, and help to ensure that the study does not progress from one phase to the next without sufficient evidence of success.

Table 2. Monitoring and success criteria for pilot study

Research objective	Criterion	Description	RAG scores
Evaluability	Eligible referral volume	Number of months (out of 7 recruitment months) where at least one Borough achieves a 'critical mass' of 30 eligible referrals where we can initiate the study onboarding and randomisation process for a cohort of parents/caregivers. ¹⁷ (OR a critical mass of 30 eligible referrals is achieved across all 3 Boroughs combined, provided those participants have indicated that they are content with online delivery).	Green: 5-6 months Amber: 3-4 months Red: 0-2 months
	Baseline data collection and randomisation	Number of participants who are randomised (and meet the requirements to be randomised, i.e. they're eligible, they've consented, they have complete referral information, and they complete baseline surveys).	Green: 92+ participants (over 2/3rds of 138 target) Amber: 47-92 (up to 2/3rds of target) Red: 0-46 (up to 1/3rd of 138 target)
	Evaluation retention - treatment	Proportion of participants randomised to the treatment group who submit the post-intervention survey. These thresholds are based on the EIF evidence standards guidelines .	Green: 90-100% of participants randomised to treatment Amber: 35-89% Red: <35%
	Evaluation retention - control	Proportion of participants randomised to the control group who submit the post-intervention survey.	Green: 90-100% of participants randomised to control Amber: 35-89% Red: <35%
Outcomes	Outcomes	Directional change in outcome variables for treatment and control.	Green: At least one outcome

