¹⁷ We are intending to conduct 7 tranches of randomisation and run 7 GenPMTO groups, one each month between December 2024 and June 2025. Based on conversion rates identified in the previous study stages, we anticipate that each tranche will require 30 eligible referrals (210 across all tranches), which we anticipate will result in approximately 20 participants completing baseline surveys and being randomised (138 across all tranches). We aim for no more than 15% attrition, with 17 completing post-test surveys (achieving our target of 120 completed pre- and post-test outcome surveys across the 7 cohorts). To run an in-person GenPMTO group, we will require 30 eligible referrals within one Borough. To run an online GenPMTO group, we will only require 30 eligible referrals combined across all 3 Boroughs (given that proximity to a physical location will not be an important factor for online delivery). However, these 30 participants need to indicate that their preference is to receive the programme online (or indicate that they have no preference).

		Where null results are those where 95% confidence intervals (CI) include 0, and positive/negative results are those where 95% CIs are entirely above or below 0 (depending on how the variable is coded and which direction is considered an improvement to the outcome).	measure indicates positive results, and none indicate negative results Amber: Null or mixed results Red: At least one outcome measure indicates negative results and no positive results
Deliverability	Programme completion	Proportion of participants randomised to GenPMTO who complete a sufficient proportion of the intervention (defined by developers as attending at least 8 sessions). We will monitor programme take-up and continued attendance throughout the study to identify if we are on track to meet these targets. Note that we will attempt to retain all randomised families in the evaluation, regardless of their attendance.	Green: 80-100% of participants randomised to GenPMTO Amber: 50-79% Red: <50%
	Fidelity	The proportion of practitioners achieving an aggregate mean Fidelity of Implementation Rating System (FIMP) score of at least 4, as rated by ISII programme experts. A FIMP score of 4 is considered to be the lowest score for what is considered acceptable implementation fidelity.	Green: 80-100% of practitioners Amber: 60-79% Red: <60%

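### Two rows of Table 2 have faulty RAG cut-points: the planned 7 of 7 referral months has no printed band, and 92 randomised families fall in both Green and Amber

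*Protocol*

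**What the plan says.** Section 4 of the protocol sets Red, Amber and Green bands in Table 2, to be rated monthly and used in the recommendation to the funder on Stage 4. Amber calls for delivery to be reviewed or adjusted; Red calls for a pause.

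- **Eligible referral volume.** The score is defined as "Number of months (out of 7 recruitment months) where at least one Borough" (or, for online delivery, all boroughs combined) reaches 30 eligible referrals. Its bands are "Green: 5-6 months Amber: 3-4 months Red: 0-2 months". Footnote 17 gives the plan: "We are intending to conduct 7 tranches of randomisation and run 7 GenPMTO groups, one each month between December 2024 and June 2025". The Section 11 timeline also lists seven monthly cohorts.
- **Baseline data collection and randomisation.** The upper bands are "Green: 92+ participants (over 2/3rds of 138 target) Amber: 47-92 (up to 2/3rds of target"). Red is 0-46, glossed as up to one third of 138.
- **Percentage rows.** Retention in the treatment arm has "Green: 90-100% of participants randomised to treatment Amber: 35-89" per cent, with the same cuts for control. Completion has "Green: 80-100% of participants randomised to GenPMTO Amber: 50-79" per cent. Fidelity and acceptability have Green from 80% and Amber 60-79%. The Red cuts in these rows are strict inequalities: below 35%, 50% or 60%.

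**The concern.** Pre-set bands should give every attainable value exactly one rating. Two rows do not. The referral scale runs to 7 but its bands stop at 6, so the intended result is the one value left unrated. The randomisation scale rates 92 twice, and the number printed for Green disagrees with the words beside it. At 92, someone must decide after seeing the count whether the criterion is Green (no action) or Amber (review or adjust delivery). That is the choice that thresholds fixed in advance are meant to remove.

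**Working it through.** **Inputs.** Maximum referral score 7 (Table 2); planned tranches 7 (footnote 17, Section 11); randomisation target 138 (Table 2, footnote 17); bands as printed.

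**Reproducing the protocol's cut-points.** 138 × 1/3 = 46.0 and 138 × 2/3 = 92.0. Both are exact, so the printed 46 and 92 are the intended fractions and no rounding is involved.

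**Referral row, every possible value.**

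| Months | Printed band |
|---|---|
| 0, 1, 2 | Red |
| 3, 4 | Amber |
| 5, 6 | Green |
| 7 | none |

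**Randomisation row, values around the cuts.**

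| Randomised | Printed band |
|---|---|
| 46 | Red |
| 47 | Amber |
| 91 | Amber |
| 92 | Amber and Green |
| 93 | Green |

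Across all counts from 0 to 210 (7 × 30 eligible referrals), 92 is the only one without a single rating. The glosses settle where it belongs. Green means more than two thirds, which starts at 93. Amber means up to two thirds, which includes 92. The lower cut follows the same convention: up to one third includes 46, and Amber starts at 47.

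**Percentage rows.** If arms were equal (an assumption), each would hold 138/2 = 69.

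- Retention: 62/69 = 89.86%, above 89% and below 90%.
- Completion: 55/69 = 79.71%, above 79% and below 80%.

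Unrounded, neither value has a band. Rounded to whole per cent, they become 90% and 80%, both Green. The picture depends on arm size:

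- With 70 in an arm, the nearest counts give 62/70 = 88.57% and 63/70 = 90.00% for retention, and 55/70 = 78.57% and 56/70 = 80.00% for completion.
- With 71, they give 63/71 = 88.73% and 64/71 = 90.14%, and 56/71 = 78.87% and 57/71 = 80.28%.

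At those two sizes no count falls in either interval.

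**The case against.** The strongest reply is that little turns on this. Nobody would rate 7 of 7 below Green on a scale where more months is better, and that score can only be reached in the last recruitment month, so it cannot disturb earlier monthly ratings. The section on insufficient power speaks of 6 or more tranches, so the 5-6 band may be left over from a six-tranche plan (an inference). Section 4 also says that the ratings guide an overall judgement, alongside qualitative evidence, with no fixed rule on how many of each colour permit progression. All of this stands and limits the weight of the point. It does not make either cell correct, and at 92 there is no obvious reading to fall back on other than the gloss.

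A reader might also infer that the percentage rows contain gaps of the same kind. The document does not support putting it that strongly. These bands are printed in whole per cents, and rounding to whole per cents closes them. A rounding convention may properly be left to the analysis plan. The 69 per arm used above is not a protocol figure, since simple randomisation does not fix arm sizes. For fidelity, a value strictly between 79% and 80% needs at least 24 practitioners (19/24 = 79.17%), and the protocol does not give the number of practitioners. For the same reasons, a probability of landing in such a gap would not be informative: it would have to assume equal arms and a true rate at the cut itself.

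**Conclusion.** The point holds for two cells of Table 2. The referral row omits the planned score of 7, and the randomisation row gives 92 two ratings, with Green's number at odds with its own description. Both follow from the printed figures with no outside assumption. Each affects one value on its scale, at or above the Green/Amber boundary. The percentage rows merit only a clearer way of writing the cut.

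A reader might go further and infer that the progression decision, or a pause in delivery, hangs on these errors. The document does not support that. No affected value touches a Red cut, the Red cuts have neither gap nor overlap, and progression is not tied to a count of ratings. This is a minor correction worth making.

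**What to change.** Edit the two rows so that each value has one rating, following the table's own glosses:

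- **Referral volume:** Green 5-7, Amber 3-4, Red 0-2 months.
- **Number randomised:** Green 93 or more, Amber 47-92, Red 0-46.

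As a tidy-up, write the percentage Amber bands with strict upper limits, matching the way the Red cuts are already written:

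- **Retention, both arms:** Amber 35% to <90%.
- **Completion:** Amber 50% to <80%.
- **Fidelity and acceptability:** Amber 60% to <80%.

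Unrounded values such as 89.9% or 79.7% would then be Amber without a rounding rule. If whole-per-cent rounding is what is intended, one sentence saying so would do instead.

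The cost is a few cell edits in one table. Data collection, conduct and sample size do not change.
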